1. PROTOCOL SUMMARY

1.1. Synopsis

Protocol Title: Phase IIb Multi-Center, Randomised, Partial-Blind, Parallel Cohort Study to Assess the Efficacy and Safety of Treatment with GSK3228836 in Participants with Chronic Hepatitis B Virus (B-Clear)

Short Title: Phase IIb study of GSK3228836 in Participants with Chronic Hepatitis B (B-Clear)

Rationale:

Study 209668 is intended to evaluate if treatment with GSK3228836 can achieve sustained virologic response (SVR, HBsAg <lower limit of quantitation [LLOQ] and HBV DNA <LLOQ sustained for 24 weeks post-GSK3228836 treatment end) with a finite course of GSK3228836. In addition, the study will evaluate the safety, tolerability, pharmacokinetic and pharmacodynamic properties of GSK3228836 in the four dosing regimens.

Key Objectives and Estimand/Endpoints:

Objectives	Estimand/Endpoints
Primary	
Efficacy: To assess the efficacy of the three dosing regimens of GSK3228836 in participants with CHB	Primary estimands supporting the primary objective are defined as: - Population: separate assessment for the following: - participants with CHB on stable nucleos(t)ide therapy - participants with CHB not currently on nucleos(t)ide therapy - Variable: Participants achieving sustained virologic response (SVR, described in Section 9.4.2) for 24 weeks after the planned end of GSK3228836 treatment in the absence of rescue medication. - Treatments: arms 1, 2, and 3. Estimation of the within-arm response rate. - Intercurrent events: use of rescue medication, and discontinuation of/interruption of/adherence to IP. The use of rescue medication has been incorporated into the definition of variable (composite strategy). Discontinuation of, interruption of, and adherence to IP will be ignored (treatment policy). Wide disruptive events (such as COVID-19 pandemic) leading to discontinuation of, interruption in, and non-adherance to GSK3228836 will be handled assuming they had not happened (hypothetical strategy). - Population summary: proportion of participants who achieve SVR for each treatment arm.

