8. STUDY ASSESSMENTS AND PROCEDURES

- Study procedures and their timing are summarized in the SoA.
- In selected sites/countries, participants will have the option to use a centralised home nursing provider. Only selected visits will have the option to be performed as a home visit, these will include drug administration, blood draws, participant assessments

and data collection. The full specifications of the home nursing services will be outlined in the SRM

- Protocol waivers or exemptions are not allowed.
- Immediate safety concerns should be discussed with the sponsor immediately upon occurrence or awareness to determine if the participant should continue or discontinue study intervention.
- Adherence to the study design requirements, including those specified in the SoA, is essential and required for study conduct.
- All screening evaluations must be completed and reviewed to confirm that potential participants meet all eligibility criteria. The investigator will maintain a screening log to record details of all participants screened and to confirm eligibility or record reasons for screening failure, as applicable.
- Procedures conducted as part of the participant's routine clinical management (e.g., blood count) and obtained before signing of ICF may be utilized for screening or baseline purposes provided the procedure met the protocol-specified criteria and was performed within the time frame defined in the SoA.
 - Repeat or unscheduled samples may be taken for safety reasons or for technical issues with the samples.

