8.1. Efficacy Assessments

The primary objective measurements for efficacy include:

- HBsAg
- HBV DNA

HBsAg and HBV DNA are collected as per the SoA. Details of sample collection can be found in the SRM.

The primary efficacy endpoint is sustained virologic response, which is a composite endpoint defined as HBsAg <LLOQ and HBV DNA <LLOQ at the end of GSK3228836 treatment which is sustained for 24 weeks post-GSK3228836 treatment. Seroclearance refers to participants with HBsAg and HBV DNA <LLOQ (with or without the formation of HBs-antibody). Seroconversion refers to participants with HBsAg and HBV DNA <LLOQ plus formation of HBs-antibody. Both terms are used to evaluate efficacy. For the purposes of this study, sustained response is defined as a continuous 24 weeks from end of GSK3228836 treatment during which levels of HBsAg in serum remain less than LLOQ and HBV DNA less than LLOQ.

Any HBsAg greater than LLOQ or HBV DNA greater than LLOQ after achieving HBsAg seroclearance and HBV DNA suppression needs to be confirmed by re-test within 1 week of receiving the test result. The re-test result will be used if the first test is not confirmed.

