9.4.2. Primary Endpoint(s)

Analyses will be conducted separately for the on nucleos(t)ide treatment and not currently on nucleos(t)ide treatment populations. The primary analysis for the primary

endpoint will be conducted once the last participant has completed the Week 48 visit and database lock has been achieved.

The primary efficacy endpoint is achieving a sustained virologic response for 24 weeks after the planned end of GSK3228836 treatment in the absence of rescue medication. Sustained virologic response is defined as observing HBsAg <LLOQ and HBV DNA <LLOQ at each analysis window in the 24 weeks after the end of GSK3228836 treatment. Analysis windows for the post GSK3228836 treatment assessments will be defined in the analysis plan.

HBsAg and HBV DNA from Week 24 to Off-Treatment Week 24 will be used to assess the primary endpoint for arms 1 and 2, and the exploratory endpoint for arm 4. For dosing schedule of arms 1, 2, and 4, see Section 4.1.

For arm 3, because of the shortened time on treatment (12 weeks instead of 24 weeks), post-treatment visit schedules will not match those of arms 1 and 2. To avoid risk of bias the following visits have been selected for arm 3 to match the number and timing of visit windows for measuring off-treatment virologic responses in arms 1 and 2 to evaluate the primary endpoint

o Week 12, 13, 14, 16, 20, 24, off-treatment Week 4, 8, 12

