4.2.2.1. Visit windowing and multiple measurements at one analysis timepoint

Visit windowing for the primary endpoint will be applied as specified in Table 2 and Table 3 and the windowed results will be used to determine the primary endpoint of SVR. Unscheduled assessments will be included in the analysis window. No imputation of missing data will be performed prior to visit windowing.

If there are multiple values within an analysis window the following rules will be applied:

For the End of '836 Treatment Analysis Timepoint:

1. The latest available assessment in the window will be selected.

For Post '836 Treatment Analysis Timepoints:

- 1. Worst non-missing value in the analysis window will be selected, if values are the same then the value closest to target day will be selected. If there are multiple values equidistant from the target day, the earliest will be selected. If all values within an analysis window are missing, then the result is missing for the analysis window.
- 2. Worst value is defined in the order of: highest actual value, then <LLOQ, and then TND.

Table 2 Primary endpoint analysis windows for Arms 1, 2 and 4

Analysis	Parameter	Target	Analysis	Window	Analysis	Protocol
Set / Domain	(if applicable)	Study Day	Beginning Timepoint	Ending Timepoint	Timepoint	Visit
Efficacy	HBsAg and HBV DNA	162	148	182	End of '836 Treatment	Week 24
		218	183	238	Post '836 treatment Week 8	Off treatment Week 8
		274	239	294	Post '836 treatment Week 16	Off treatment Week 16
		330	295	350	Post '836 treatment Week 24	Off treatment Week 24

Table 3 Primary endpoint analysis windows for Arm 3

Analysis	Analysis Parameter		Analysi	s Window	Analysis	Protocol
Set / Domain	(if applicable)	Study Day	Beginning Timepoint	Ending Timepoint	Timepoint	Visit
Efficacy	HBsAg and HBV DNA	78	64	98	End of '836 Treatment	Week 12
		134	99	154	Post '836 treatment Week 8	Week 20
		190	155	210	Post '836 treatment Week 16	Off treatment Week 4
		246	211	266	Post '836 treatment Week 24	Off treatment Week 12

The primary analysis will be based on planned end of treatment regardless of whether a patient discontinued treatment early.

For the second supplementary estimand described in Section 4.2.4.2, SVR will be measured from actual rather than planned end of treatment and the analysis windows should be amended accordingly. For this estimand, the date of last dose should be treated as the reference date and the rules in Table 4 should be used to determine the endpoint of SVR.

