4.2.2.2. Intercurrent Events and Missing data

The intercurrent event of use of rescue medication has been incorporated into the definition of variable (composite strategy). The intercurrent event of discontinuation of, interruption of, and adherence to IP not due to wide disruptive event will be ignored (treatment policy).

To prevent the efficacy of GSK3228836 being penalized for uncontrollable and unusual events (i.e. wide disruptive events such as the COVID-19 pandemic), if a wide disruptive event leads to discontinuation of GSK3228836 or significant interruption/non-adherence to GSK3228836, this will be handled assuming the intercurrent event had not happened (hypothetical strategy). Significant interruption/non-adherence is defined as a gap of >=21 days between treatment doses at any time during the on-treatment period. According the hypothetical strategy, any data collected after the intercurrent event will be set to missing.

If all analysis windows have non-missing response information, a participant's response (Responder or Non-responder) is determined as follows:

- 1. If rescue medication was used, then the participant is a non-responder.
- 2. If HBsAg <LLOQ and HBV DNA <LLOQ in each of the analysis window, then the participant is a Responder, otherwise the participant is non-responder. Note: A result of TND is considered as <LLOQ.

The following approach will be used to determine a participant's response when HBsAg and HBV DNA data are missing from visits required to derive the primary endpoint:

For participants where wide disruptive events (such as COVID-19 pandemic) prevent assessment of the primary outcome, SVR will be imputed using all available data for

participants for whom SVR can be assessed. The final inference from the hierarchical Bayesian model will account for the missing data assuming MAR. For other participants where SVR in the absence of rescue medication cannot be ascertained due to missing data (withdrawal from the study or missing due to other reasons, but not due to a wide disruptive event), the participant will be assumed not to have achieved SVR (non-responder imputation).

After the imputation above, if there is missing data in at least one analysis window then the participant is a non-responder.

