6.2.5. Multiple measurements at One Analysis Time Point

Multiple Measurements at One Analysis Time Point

- Handling of multiple measurements within an analysis window for primary endpoint is described in Section 4.2.2
- Assessments on unscheduled visit will not be included in the tables of summary statistics by visit but
 will be included in the associated listings. Also, such assessments on unscheduled visit will be used
 for the "any time on-treatment" or "Any visit post-baseline" time point.
- If there are multiple assessments on scheduled visit within visit window, will query the site to identify the valid assessment as the assessment for the scheduled visit.
- Participants having both High and Low values for Normal Ranges at any post-baseline visit for safety parameters will be counted in both the High and Low categories of "Any visit post-baseline" row of related summary tables.

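### The primary SVR derivation takes the worst post-treatment value, so a rise that the protocol's re-test does not confirm still makes a non-responder

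*SAP*

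**What the plan says.** **Protocol.** Section 8.1 defines the primary endpoint and sustained response. It then requires any HBsAg or HBV DNA above LLOQ after response to be re-tested within a week of the result being received, and settles which value counts: "The re-test result will be used if the first test is not confirmed". It does not say whether a re-test is a new blood sample or a re-assay. Section 8 allows both kinds of cause: "Repeat or unscheduled samples may be taken for safety reasons or for technical issues with the samples".

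The primary estimand (Synopsis) uses "sustained virologic response (SVR, described in Section 9.4.2) for 24 weeks after the planned end of GSK3228836 treatment". Section 9.4.2 gives SVR as "defined as observing HBsAg <LLOQ and HBV DNA <LLOQ at each analysis window in the 24 weeks after the end of GSK3228836 treatment" and leaves the windows to the analysis plan. It does not say which of two results represents a window.

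**SAP.** Section 4.2.2.1 states "Unscheduled assessments will be included in the analysis window". For post-treatment windows it states "Worst non-missing value in the analysis window will be selected", with a quantified value ranked worse than <LLOQ, and <LLOQ worse than target not detected. The end-of-treatment window takes the latest value instead and is not at issue here. Section 4.2.2.2 then classifies: "If HBsAg <LLOQ and HBV DNA <LLOQ in each of the analysis window, then the participant is a Responder"; anyone else is a non-responder.

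Section 6.2.5 adds nothing: "Handling of multiple measurements within an analysis window for primary endpoint is described in Section 4.2.2". A confirmation rule appears only in the fourth supplementary estimand (4.2.4.4), which accepts confirmation at the next visit, unscheduled visits included. Table 9 in Section 4.8 lists that estimand as an addition. It explains that single aberrant values have occurred, some probably through site or laboratory error, and that they cannot be resolved in the data.

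**The concern.** The protocol and the SAP give two rules for the same primary endpoint, and the rules can classify the same participant differently. Under protocol 8.1 a re-test <LLOQ displaces the first value. Under SAP 4.2.2.1 it cannot: the re-test is added to the window and the higher first value still wins. The SAP does not mention the difference, and Table 9 presents confirmation as a new, modified definition although the protocol already had a re-test rule.

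The primary output is an estimated SVR rate with a credible interval, and the same rates feed the comparisons and regimen selection in SAP 4.3.1.2. A rule that can only lower the rate relative to the protocol rule therefore affects the main result. The documents do not show whether unconfirmed rises are errors or real transient rises, so this is a downward shift relative to 8.1, not a demonstrated bias.

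**Working it through.** **1. One participant under each rule.** Take a participant in Arm 1 with a quantified HBsAg at day 218, a repeat sample <LLOQ at day 225, and everything else <LLOQ without rescue medication. Both days lie in the day 183–238 window of SAP Table 2.

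- Protocol 8.1: the rise is not confirmed, the re-test is used, and the participant is a responder.
- SAP 4.2.2.1 and 4.2.2.2: the worst value is the day 218 result, the window fails, and the participant is a non-responder.
- SAP 4.2.4.4: the rise is not confirmed, so the participant is a responder, but only in that supplementary analysis.

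**2. Reproducing the plan's figures.** Inputs from SAP Section 5: n = 66 in each of Arms 1–3, prior Beta(0.5, 0.5), posterior probability above 75%. With x responders the posterior is Beta(0.5 + x, 66.5 − x). The smallest x that passes is 12, 16 and 19 for thresholds of 15%, 20% and 25%, as in Table 11. The exact binomial tails are P(X ≥ 12 | 66, 0.20) = 0.691 and P(X ≥ 16 | 66, 0.30) = 0.877, matching the stated 69% and 88%.

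**3. What one responder decides.** Posterior probability that the rate exceeds the threshold, at the minimum count and one below:

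| Threshold | At minimum | One fewer | Chance of landing exactly on the minimum |
|---|---|---|---|
| 15% | x = 12: 0.771 | x = 11: 0.660 | 11.8% (true rate 20%) |
| 20% | x = 16: 0.808 | x = 15: 0.717 | 11.3% (true rate 25%) |
| 25% | x = 19: 0.765 | x = 18: 0.672 | 10.5% (true rate 30%) |

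These use the unstratified planning model of SAP Section 5, not the hierarchical model of 4.2.2.

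**4. Exposure to the rule.** Setting the scheduled days against SAP Tables 2 and 3, the three post-treatment windows contain:

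- Arms 1 and 2: days 190, 218 / 246, 274 / 302, 330, which is 6 visits.
- Arm 3, using only the visits listed in SAP 4.2: days 106, 134 / 162, 190 / 218, 246, also 6 visits.

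**5. Illustration of size.** Let q be the chance per visit of an unconfirmed rise in either marker, independent between visits. The documents give no value for q, so 0.5%, 1% and 2% are assumptions. The share of protocol 8.1 responders lost is 1 − (1 − q)^6. With an 8.1 rate of 20%, an arm has 0.20 × 66 = 13.2 expected responders.

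| q | Share lost | Responders lost of 66 | 69% becomes | 88% becomes |
|---|---|---|---|---|
| 0.5% | 3.0% | 0.4 | 65% | 84% |
| 1% | 5.9% | 0.8 | 60% | 80% |
| 2% | 11.4% | 1.5 | 51% | 71% |

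The last two columns repeat the tails of step 2 with the rate multiplied by (1 − q)^6. They treat the tabulated true rate as the rate under the 8.1 rule.

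**6. A separate point on Arm 3.** The windowing text does not itself restrict Arm 3 to the listed visits. If every scheduled visit inside the Table 3 windows counted, Arm 3 would have 8 + 5 + 2 = 15 post-treatment visits, and the same q values would give losses of 7.2%, 14.0% and 26.1%. The conclusion here does not depend on this.

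**The case against.** The strongest case is that the SAP follows the definition the estimand cites. Protocol 9.4.2 has no confirmation step, and 8.1 itself speaks of levels staying below LLOQ for a continuous 24 weeks. The tension is then partly inside the protocol. That is fair, and 9.4.2 should be reconciled too. But 9.4.2 does not choose between two results in one window, whereas 8.1 does. Those two sections can be read together; 8.1 and SAP 4.2.2.1 cannot.

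The first value might also be replaced before windowing, in data management or programming documents not available here. That would remove the conflict. Neither the protocol nor the SAP says it happens, and Table 9 suggests that some aberrant values remain.

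Estimand 4.2.4.4 will show readers a confirmed version. It does, but the primary result stays as it is, and confirmation at a consecutive visit is not the same as the one-week re-test.

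Three points stand. No document shows a participant actually classified differently: Table 9 does not say how many aberrant values had a re-test <LLOQ. The size rests on assumed q. And the present rule is conservative, while changing it can only leave SVR the same or raise it, after aberrant values are already known. That makes disclosure of timing essential, but it does not justify leaving two contradictory rules in place.

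**Conclusion.** The point holds and must be fixed. As written, the primary derivation overrides the protocol's rule on unconfirmed rises in the three post-treatment windows without saying so. It applies whenever the first value is kept in the data.

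The direction is downward relative to protocol 8.1, and the actual size is unknown. The wording conflict is certain; its effect on the reported rate is not. At the planned arm size a single reclassified participant can reverse any of the three criteria. The illustrative loss of about 0.4 to 1.5 responders per arm assumes 0.5% to 2% unconfirmed rises per visit, independence, six visits and a 20% rate under the 8.1 rule.

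**What to change.** - In SAP 4.2.2.1, before the worst value is chosen, replace a value at or above LLOQ by its linked protocol 8.1 re-test when that re-test is <LLOQ.
- State whether a re-test means a new sample, a re-assay, or either. Let a re-test dated in the next window still apply to its original value, because the one-week clock starts when the result is received.
- Keep a value with no re-test, or none that can be linked, as a failure.
- Report the present worst-value version as a sensitivity analysis.
- In SAP 4.8, record how protocol 8.1 and 9.4.2 and SAP 4.2.2.1 and 4.2.4.4 relate, and when the change was made relative to the third interim and to sponsor unblinding (protocol 9.5).
- As a side clarification, state with Table 3 that only the Arm 3 visits listed in SAP 4.2, and their re-tests, enter the windows.

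The cost is SAP wording, one derivation step and one sensitivity table. The protocol already requires the re-tests, but they must be linkable to the values they check. The drawback is that the primary SVR can only stay the same or rise, which is why the timing has to be disclosed.

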Pregnancy test (women of child bearing potential)	Х		Х	X	X	Х	Х	Х	Х
Hematology ² [includes platelet count and WBC]	Х	Х	Х	Х	Х	Х	Х	Х	Х
PT, INR, aPTT	Х		Х		Х	Х	Х	Х	Х
Chemistry	Х	Х	Х	Х	Х	Х	Х	Х	Х
Urinalysis	Х	Х	Х	Х	Х	Х	Х	Х	Х
Urine ACR	Х	Х	Х	Х	Х	Х	Х	Х	Х
HBsAg and HBV DNA	Х	Х	Х	Х	Х	Х	Х	Х	Х
Anti- HBsAg	Х	Х	Х	Х	Х	Х	Х	Х	Х
Anti- HBeAg	Х	Х	Х	Х	Х	Х	Х	Х	Х
HBeAg (only for participants HBeAg positive at screening)	Х	Х	Х	Х	Х	Х	Х	Х	Х
HBV RNA, HBcrAg, and Sequencing (HBV Genotype/phenotype; HBV DNA and/or RNA)	Х		Х		X		Х	Х	Х
Complement C3, Complement C4, hs-CRP, MCP-1		Х	Х	Х	Х	Х	Х	Х	Х

Assessments ¹	OT-Day 1	OT-Day 8	OT-Day 22	OT-Day 50	OT-Day 78	OT-Day 106	OT-Day 134	OT-Day 162	Early Termination
Window	±3 E	ays			±10	Days			
	OT- W1	OT-W2	OT-W4	OT-W8	OT-W12	OT-W16	OT-W20	OT-W24	
Complement C5a, Complement factor Bb		Х	Х	Х	Х	Х	Х	Х	Х
ANCA, Ang II	Х		Х	Х	Х	Х	Х	Х	Х
PK	Х	Х	X	X	X	Х	Х	Х	Х
PBMC Collection for immunophenotyping ³	Х				Х			Х	Х
Soluble Protein (immunology)	Х		Х		Х		Х	Х	Х
PAXGene RNA for expression analysis in whole blood	Х				Х			Х	Х
APRI/Fibrosure								Х	Х
Archived Samples [serum; plasma]	Х	Х	Х	Х	Х	Х	Х	Х	Х

- 1. In selected countries/sites, participants will have the option to use a centralised home nursing provider. Only selected visits will have the option to be performed as a home visit, these will include drug administration, blood draws, participant assessments and data collection. The full specifications of the home nursing services will be outlined in the SRM.
- 2. Hematology- platelet count analyzed at local laboratory is **optional** during the off-treatment period; hematology samples to be collected for central laboratory assessments (required; if local lab is being drawn, in parallel with local lab sample).
- 3. Only for selected sites able to transport to the analysis lab as specified in the SRM.

OT: off-treatment; the first off-treatment visit occurs 7 days after the last study treatment dose received, whether planned or last dose given after participant is withdrawn from study treatment (e.g., the planned first off-treatment visit occurs on Day 169, 7 days after the Day 162 visit; if participant is withdrawn from study treatment on Day 50, the first off-treatment visit occurs on Day 57)

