4.2. Primary Endpoint(s) Analyses

The primary analysis for the primary endpoint will be conducted once the last participant has completed the Week 48 visit and database lock has been achieved.

An estimation approach with no hypothesis testing will be used to address the primary objective. The primary assessments of interest are the point estimate of SVR rate and 95% credible intervals; in addition, posterior probabilities that the true SVR rate in each treatment arm is greater than a range of clinically meaningful response rates will be provided. The point estimates for SVR will be calculated using a Bayesian probability approach. Comparisons between treatment arms as defined in the key secondary/exploratory objectives will be assessed using probability inference approaches.

The primary efficacy endpoint is achieving a sustained virologic response for 24 weeks after the planned end of GSK3228836 treatment in the absence of rescue medication. Sustained virologic response is defined as observing HBsAg <LLOQ and HBV DNA <LLOQ at each analysis window in the 24 weeks after the end of GSK3228836 treatment. Analysis windows for the post GSK3228836 treatment assessments are defined in Section 4.2.2.1.

HBsAg and HBV DNA from Week 24 to Off-Treatment Week 24 will be used to assess the primary endpoint for arms 1 and 2, and the exploratory endpoint for arm 4. For dosing schedule of arms 1, 2, and 4, see Section 1.2.

For arm 3, because of the shortened time on GSK3228836 treatment (12 weeks instead of 24 weeks), post-treatment visit schedules will not match those of arms 1 and 2. To avoid risk of bias the following visits have been selected for arm 3 to match the number and timing of visit windows for measuring off-treatment virologic responses in arms 1 and 2 to evaluate the primary endpoint:

o Week 12, 13, 14, 16, 20, 24, off-treatment Week 4, 8, 12.

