4.2.4.4. Using a Modified Definition of SVR

The fourth supplementary estimand is defined in the same way as the primary estimand, except the variable is defined using a modified definition of sustained virologic response (SVR) for 24 weeks after the planned end of GSK3228836 treatment in the absence of rescue medication. The modified definition of sustained virologic response is defined as

observing HBsAg <LLOQ and HBV DNA <LLOQ at each analysis window in the 24 weeks after the end of GSK3228836 treatment. Any observation of HBsAg ≥LLOQ or HBV DNA ≥LLOQ must be confirmed at a consecutive visit (including unscheduled visits) for the patient to be classed as having lost their SVR.

Subjects who have a value of HBsAg ≥LLOQ or HBV DNA ≥LLOQ at their last visit, which cannot be confirmed due to no further follow up, will be treated as non-responders.

This supplementary estimand supporting the primary objective in participants with CHB on stable nucloes(t)ide therapy and participants with CHB not currently on nucleos(t)ide therapy is the proportion of participants in each treatment arm 1, 2, 3 and 4 who achieve the modified definition of SVR for 24 weeks after the planned end of GSK3228836 treatment in the absence of rescue medication, regardless of completing IP, interruptions in IP or adherence to IP, had they not been affected by wide disruptive events.

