6.2.2. Assessment Windows

Refer to Section 4.2.2.1 for details of visit windowing for the main efficacy estimands.

Unless otherwise specified, no windowing will be applied to unscheduled visits. Planned time relative to dosing will be used in figures, summaries, statistical analyses and calculation of any derived parameters, unless otherwise stated. Unscheduled visits will not be included in summary tables and/or figures except from determining response for primary endpoint as described in Section 4.2.2.1 and summaries over "any time on treatment" or "any visit post-baseline". Unscheduled visits will be included in listings.

Laboratory and vital signs data collected at Early Termination Visits will be assigned to assessment windows, according to the actual date.

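### The SVR windowing in SAP 4.2.2.1 applies neither the nine-visit Arm 3 list nor the protocol re-test rule, so Arm 3 has 15 scheduled chances of a disqualifying value against 6 in the other arms

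*SAP*

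**What the plan says.** Protocol 9.4.2 and SAP 4.2 list the Arm 3 visits for the primary endpoint: Weeks 12, 13, 14, 16, 20 and 24 and off-treatment (OT) Weeks 4, 8 and 12. The reason given is "To avoid risk of bias the following visits have been selected for arm 3 to match the number and timing of visit windows" used for Arms 1 and 2.

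Protocol 8.1 requires a re-test of any value above LLOQ seen after clearance, and adds: "The re-test result will be used if the first test is not confirmed". The same section says "sustained response is defined as a continuous 24 weeks from end of GSK3228836 treatment".

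SAP 4.2.2.1 derives SVR from the windows in Table 2 (Arms 1, 2 and 4) and Table 3 (Arm 3). For post-treatment windows the rule is "Worst non-missing value in the analysis window will be selected", with the highest actual value ranked worst. It also says "Unscheduled assessments will be included in the analysis window". SAP 6.2.2 repeats this: unscheduled visits stay out of summaries "except from determining response for primary endpoint as described in Section 4.2.2.1" and a few any-time summaries.

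SAP 4.2.4.4 requires confirmation of a value at or above LLOQ, but only in a supplementary estimand with a modified definition of SVR. SAP 4.8, which records changes from the protocol, lists that estimand as an addition. It does not say that the Arm 3 list or the re-test rule has been dropped.

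**The concern.** Two rules in force elsewhere do not reach the section that would be programmed.

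First, Arm 3 takes placebo in Weeks 13 to 24, so HBsAg and HBV DNA are still measured weekly for 12 weeks after its GSK3228836 ends. Arms 1, 2 and 4 move to the sparser off-treatment schedule. Tables 2 and 3 match the number and timing of the windows but not the number of values inside them. With a worst-value rule, each extra value is another chance to fail.

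Second, an unconfirmed value that protocol 8.1 would replace stays in the window beside its re-test, and the worst-value rule selects it. This affects every arm, and it also decides how much the Arm 3 imbalance matters. Lasting rebound is detected on any reading; only isolated values are at issue. SAP 4.8 says such values have occurred and cannot be resolved, without saying in which arm or period.

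There is an effect in the other direction. Under SAP 4.2.2.2 a missing window means non-response (unless a wide disruptive event caused it), and denser sampling leaves fewer windows empty.

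At stake are the Arm 3 SVR rate, the comparisons 1 v 3, 2 v 3 and 3 v 4, and the regimen selection in SAP 4.3.1.2, which rests on a -5% margin.

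**Working it through.** **Visit days.** From the Schedule of Activities, HBsAg and HBV DNA are taken weekly to Day 162 and then at OT Days 169, 176, 190, 218, 246, 274, 302 and 330.

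**The plan's own matching reproduces.** The Arm 3 list is Days 78, 85, 92, 106, 134, 162, 190, 218, 246. Arms 1 and 2 use Days 162, 169, 176, 190, 218, 246, 274, 302, 330. Measured from the planned last dose (Day 78 or Day 162), both give 0, 7, 14, 28, 56, 84, 112, 140 and 168 days.

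**Scheduled values in the post-treatment windows, nominal days, dosing completed:**

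| Window | Arms 1, 2, 4 (Table 2) | Arm 3 as written (Table 3) | Arm 3, listed visits only |
|---|---|---|---|
| Post Week 8 | 190, 218 | 99, 106, 113, 120, 127, 134, 141, 148 | 106, 134 |
| Post Week 16 | 246, 274 | 155, 162, 169, 176, 190 | 162, 190 |
| Post Week 24 | 302, 330 | 218, 246 | 218, 246 |
| Total | 6 | 15 | 6 |

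Within the visit tolerances (3 days up to OT Week 2, 10 days after) the counts are 14 to 16 against 5 to 6. If injections stop early the OT visits move, because "the first off-treatment visit occurs 7 days after the last study treatment dose received". With a last injection at Day 134 the counts are 8+2+2 = 12 against 2+2+1 = 5. The end-of-treatment windows are balanced: five scheduled values each, the latest selected (Day 92 or Day 176, both 14 days after the planned last dose).

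**Illustration of size (all rates assumed).** Let q be the chance that one visit's value is falsely at or above LLOQ, m the missed-visit rate and k the number of values in a window. A true responder is kept with probability equal to the product over windows of (m + (1-m)(1-q))^k - m^k. With m = 0 this is (1-q)^6 against (1-q)^15. At q = 1%: 0.9415 against 0.8601, and 30 x 0.0814 = 2.4 points. For correlated errors, q becomes a Beta-distributed participant rate Q with mean q and intraclass correlation 0.1 or 0.3. For the re-test rule, Q is replaced by Q squared.

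Difference in SVR points at true SVR 30% (positive = against Arm 3):

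| Assumptions | q = 0.1% | 0.5% | 1% | 2% |
|---|---|---|---|---|
| No confirmation, m = 0, independent | 0.3 | 1.3 | 2.4 | 4.4 |
| Same, correlation 0.1 | 0.1 | 0.6 | 1.2 | 2.3 |
| Same, correlation 0.3 | 0.05 | 0.3 | 0.5 | 1.0 |
| No confirmation, m = 10%, independent | -0.4 | 0.6 | 1.6 | 3.5 |
| Same, correlation 0.3 | -0.5 | -0.3 | -0.1 | 0.4 |

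With the re-test rule and m = 0 the difference is at most 0.11 (independent) or 0.42 (correlated). With the re-test rule and m = 10% it is -0.6 to -0.2. Missed visits alone (m = 10%) leave at least one empty window for 2.97% of participants with 6 values and 1.00% with 15, so 30 x (0.0100 - 0.0297) = -0.59 points.

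**Non-inferiority rule.** I took Arm 3 against Arm 1 with 66 per arm, independent Beta(0.5, 0.5)-binomial posteriors, and success if P(difference > -5%) > 65%, summed exactly over outcomes. At equal true SVR of 30% and matched sampling the rule is met with probability 61%. For q = 0.1/0.5/1/2%, no confirmation and no missed visits:

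- independent errors: 60/55/49/39%
- correlation 0.1: 61/58/55/50%
- correlation 0.3: 61/60/59/57%

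With the re-test rule it is 59 to 61%, or 62 to 64% with 10% missed visits.

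**The case against.** **The list may be a filter.** SAP 4.2.2.1 sits under 4.2, the list is still in force there, and 4.8 does not drop it. Read together, 4.2 chooses the visits and 4.2.2.1 windows them, giving 6 against 6. That reading is possible, but 4.2.2.1 does not state it, so two programmers could derive different primary endpoints.

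**The windows do match.** Tables 2 and 3 have the same number, offsets and widths, which meets the literal aim. But the stated purpose is to avoid bias, and under a worst-value rule the number of values per window matters.

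**The re-test rule could act before windowing.** It could, and 4.2.4.4 asks for confirmation at a consecutive visit, which is a different test. Yet 4.2.2.1 as written keeps the unconfirmed value, and presenting confirmation as a modified definition suggests that the primary derivation has none.

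**Size and sign are not established.** This stands. The largest figures need a 2% error rate, independence, no missed visits and no confirmation together. The non-inferiority figures are single-pair, unconditional on the success rule, and not the SAP's hierarchical model or decision tree.

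**Restricting Arm 3 discards data.** Settling the re-test rule alone removes most of the imbalance, and counting every Arm 3 rebound is conservative when the rule favours the less intensive arm. The cost is real. But making all values primary would go against the list that both documents adopt to avoid bias.

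**Conclusion.** The concern holds. SAP 4.2.2.1 as written conflicts with two stated rules for the primary endpoint, and SAP 4.8 declares neither departure. The count of 15 against 6 is firm for nominal days and completed dosing, provided the list is not read as a prior filter.

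The size of any bias cannot be had from the documents, because they give no false-value or missed-visit rate. Over the assumptions above, at true SVR 30%, it runs from 0.6 points in favour of Arm 3 to 4.4 points against it. It is small if the re-test rule is applied or errors cluster strongly within participants. It approaches the 5-point margin only in the extreme case. The estimand in SAP 4.2.4.4 mitigates the problem but is supplementary and does not restore the visit list. This should be corrected, because the primary derivation currently depends on which of the conflicting rules is programmed.

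**What to change.** 1. In SAP 4.2.2.1, reconcile the worst-value rule with the protocol 8.1 re-test rule, identically for all arms. List any departure from 8.1 in SAP 4.8.
2. State that, among scheduled visits, only the nine listed Arm 3 visits enter the Table 3 windows, and that unscheduled re-tests triggered by an unlisted Arm 3 visit do not enter. All other unscheduled values follow one rule in every arm.
3. Report the all-values version as a sensitivity analysis.

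The cost is SAP wording and programming; no new data are needed. There are two downsides. A rise seen only at an unlisted Arm 3 visit would not count in the primary derivation, although protocol 8.1 speaks of continuous response; the sensitivity analysis would show how many such cases exist. Arm 3 would also lose its lower missing-window risk: at an assumed 10% missed visits, the chance of at least one empty post-treatment window rises from 1.0% to 3.0%, equal to Arms 1 and 2.
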